10.6 Packaging and Labeling

The study drug for this study will be supplied by Golden Biotechnology Corporation for active ingredient and for final formulation and packaging. The physicochemical properties and the pharmaceutical specifications of the study drug for this study are provided in the Investigator's Brochure.²⁹ The sponsor is responsible for shipping the study drug to the study site and implementing strict inventory control for drug accountability.

The study drug will be filled in # 2 capsules (100 mg) and then packed in a light-protected polyethylene bottle and closed with a piece of polyethylene cap liner fitted in the cap for each

dispensation at Visit 1 (Day 0), 3 (Day 28), 4 (Day 42), 5 (Day 56) and 6 (Day 84), and subsequent visits for patients entering the Extension Phase. The study drug will be labeled in accordance with country-specific requirements.

10.7 Dispensing and Return of Study Drug

The study investigator and/or the designated pharmacist will be in charge of the management and dispensation of the study drug. All unused study drug must be returned to investigator at each visit. Drug accountability and inventory will be recorded in the eCRFs and the relevant study log.

Patients who participate in the Extension Phase will be given enough study drugs for one cycle. Study drug will be returned to the pharmacy if the patient discontinues study drug early.

10.8 Storage and Reconciliation of Supplies

The available stability data supports a 3-year shelf-life for antroquinol capsules when stored below 28°C and in the original package.

Antroquinol capsules are packaged in a light-protected polyethylene bottle. Investigational drug must be stored at the study site in a dry place below 28°C and protected from direct light and excessive humidity, as stated in the Investigator's Brochure.²⁹ Antroquinol will be shipped to the study site by Golden Biotechnology Corporation by express delivery. During shipping, the study drug will be packaged to maintain the temperature below 28 °C.

Patients will be instructed to store the drug at room temperature and to protect the study drug from light and excess humidity.

10.9 Concomitant Medications

The investigators may prescribe additional medications during the study, as long as these are not prohibited by the protocol ([Section 10.10](#)).

Any use of concomitant treatment must be recorded on the eCRF.

10.10 Prohibited Medications, Foods and Tobacco Use

Except for antroquinol, no other cytotoxic agents (examples listed in next paragraph), investigational drugs, active or passive immunotherapy, chemotherapy, and radiotherapy will be permitted during the study period. Simultaneous participation in other clinical treatment study protocols is not allowed.

1. Small molecule inhibitors of the tyrosine kinase of EGFR, e.g., gefitinib or erlotinib
2. Monoclonal antibody binding specifically to EGFR, e.g., cetuximab or panitumumab
3. Recombinant humanized monoclonal antibody targeting vascular endothelial growth factor, e.g., bevacizumab
4. Folate analogue metabolic inhibitor, e.g., pemetrexed

Levonorgestrel will be prohibited during the conduction of this study because it is used as internal standard in bioanalysis.

Drugs/articles known to be strong inhibitors or inducers of CYP2C19, 3A4, 2C8, and 2E1 are prohibited. Drugs with a narrow therapeutic index that are substrates of 1A2, 2B6, 2C8, 2C9, 2C19, 3A and 2D6 are also prohibited. A list of commonly known substrates, inhibitors and inducers is given in [Appendix 4](#). It should be noted that this is not an exhaustive list.

Foods which may affect the assessment of the study drug should be prohibited during the study. These foods include charbroiled food, star fruit, and grapefruit juice. Smoking is also prohibited during the study.

10.11 Treatment Compliance

A patient's treatment compliance will be assessed by the following formulae:

For each visit, except Visit 2, the compliance will be calculated:

$$[(\text{Capsules actually used}) \div (\text{number of days patients exposed to study drug} * \text{planned number of capsules per day})]$$

The number of days patients exposed to study drug is calculated as:

$$[\text{Day of last dose} - \text{Day of first dose} + 1]$$

Patients who undergo dose modifications will have their treatment compliance calculated by this formula:

$$(\text{Original dose} [(\text{Capsules actually used}) \div (\text{number of days patients exposed to study drug} * \text{planned number of capsules per day for each day patient was on original dose})]) + (\text{Modified Dose} [(\text{Capsules actually used}) \div (\text{number of days patients exposed to study drug} * \text{planned number of capsules per day for each day patient was on modified dose})])$$

Site staff will record compliance of patients with their assigned regimen. Patients are to be instructed to bring their partially used or empty bottles back for inspection at each study visit. All patients are to be reminded of the importance of compliance with their assigned regimen with an emphasis on taking their study drug on schedule (i.e., every 8 hours), and contacting the site for an appointment as soon as possible if they think they are experiencing significant toxicity.

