9.1.3.3 Visit 2 (Day 14 ± 3)

- Record concomitant medications
- Perform physical examinations
- Obtain vital signs
- Perform clinical laboratory tests (hematology, biochemistry, and urinalysis)
- Record AE and grade possible toxicity
- Calculate patient compliance

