Antroquinonol will be administered as a single agent in this study at a dose of 600 mg per day (200 mg t.i.d. administered at 8-hour intervals). This dose regimen was chosen based on results from the Phase 1 clinical study (GOLANTA20090911) involving NSCLC patients refractory to conventional treatment modalities, which reported good tolerability of antroquinonol up to 600 mg/day. The area under the plasma concentration-time curve from 0 to 24 hours (AUC_{0-24}) after single dose administration on Day 1 of the first treatment cycle (Cycle 1) increased by 18.79%, 200.1%, 215.16%, 265.19% and 396.61% at the 100, 200, 300, 450, and 600 mg dose levels, respectively, when compared with the 50 mg dose level; whereas on Day 28 of Cycle 1, the AUC_{0-24} decreased by 34.88% at the 100 mg dose level and increased by 133.58%, 141.87%, 680.65% and 562.54% at the 200, 300, 450, and 600 mg dose levels, respectively. Thus, the AUC_{0-24} was not linearly proportional to the antroquinonol dose on Day 1 and Day 28. There were no significant differences in AUC_{0-24} in the 100-300 mg dose range on Day 1 and Day 28. The highest peak concentration (C_{max}) over the 100-300 mg dose range was observed with the 200 mg dose on Day 28. One patient in the 200 mg dose group and two patients in the 600 mg dose group exhibited stable disease at the end of treatment.

Thus, in order to maintain a high drug concentration and enhance the efficacy of antroquinonol 200 mg t.i.d. (every eight hours) has been chosen as the dosage regimen for this study.

The study design is based on the assumption that within each of the KRAS tumor mutation positive and negative strata, a PFS rate at 12 weeks of 40% and 35% overall would be of interest. Further testing would not be pursued if the PFS rate at 12 weeks was less than 15%. See [Section 14.1](#) for further details.

The study drug will be administered until disease progression, occurrence of unacceptable toxicity, non-compliance or withdrawal of consent by the patient, or investigator decision to stop study drug, whichever comes first.

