9.3.3 Removal of Patients from Study or from Study Treatment

Patients may withdraw their consent to participate in the study and investigators may withdraw patients at any time without prejudice. Patients will be withdrawn from the study or study treatment if any of the conditions set below has occurred:

1. Documented disease progression according to the response criteria
2. Unacceptable toxicity
3. Patient decides to withdraw his/her informed consent
4. Investigator considers that the patient is no longer physically and/or psychologically able to remain in the study

5. Patient has developed a condition that requires treatment with a medication prohibited by the protocol
6. Patient develops adverse effects that the investigator considers a permanent cessation of the study drug is necessary
7. Non-compliance with study drug, protocol requirements, or study-related procedures
8. Patient's treatment is interrupted for more than 1 week and the investigator and Medical Monitor considers a permanent cessation of the study drug is necessary

The investigators should complete the evaluation items for the EOS Visit upon a patient's withdrawal. Tumor assessment does not need to be performed at the EOS Visit if this was conducted at the Day 84 Visit. For patients participating in the Extension Phase, the tumor assessment does not need to be performed at the EOS Visit if it has been assessed within 8 weeks of the EOS Visit. This does not include a patient who has not been treated by the study drug, such as withdrawal at Screening or at Baseline. Only the electronic Case Report Form (eCRF) required data should be completed. All patients who are withdrawn or removed will not be replaced in this study.

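### The compliance denominator in Section 10.11 stops at the last dose, so a dosing gap still open at a visit is not counted as missed

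*Protocol*

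**What the plan says.** Protocol Section 10.11 sets the timing first: "For each visit, except Visit 2, the compliance will be calculated". The ratio has "Capsules actually used" as its numerator. Its denominator is the number of days exposed multiplied by "planned number of capsules per day". The day count is then defined ("The number of days patients exposed to study drug is calculated as") as "Day of last dose" minus the day of first dose, plus 1. A second formula covers patients whose dose was modified and uses the same term for days exposed.

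The visit schedule differs from this list. Section 9.1.3.3 (Visit 2, Day 14) includes the instruction "Calculate patient compliance", and Table 9.1 marks compliance at Visit 2 as well. Table 9.1 and Section 9.1.3.2 also call for it at Visit 1 (Day 0). Drug accountability, by contrast, is not scheduled at Visit 2.

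Compliance bears on one listed decision. Section 9.3.3, item 7, gives "Non-compliance with study drug, protocol requirements, or study-related procedures" as a ground for withdrawal, without a numeric threshold and without reference to the formula in 10.11.

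**The concern.** A per-visit compliance figure should show how much of the planned drug was taken up to that visit. Here the observation window closes at the patient's own last dose. A patient who has quietly given up the capsules shortens the denominator by the very days on which doses were missed. The result depends on where a gap falls, not on how much drug was taken: a gap in mid-interval is counted in full, and a gap running up to the visit is not counted at all.

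The figure therefore fails to flag self-discontinuation and is inflated wherever it is reported or used. This is not a detail left to a statistical analysis plan, because the protocol itself fixes the formula and has it applied visit by visit. No other section adds the undosed days back into the ratio.

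The disagreement over Visit 2, and the requirement at Day 0 when dosing has only begun, is a secondary point in the same measure.

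**Working it through.** **Inputs**
- Planned dose: Section 9.2.1 states "Antroquinonol will be administered as a single agent in this study at a dose of 600 mg per day", and Section 10.6 gives 100 mg capsules. 600/100 = 6 planned capsules per day.
- Formula (10.11): compliance = capsules used / [(last-dose day − first-dose day + 1) × 6].
- Comparator: capsules used / (planned dosing days before the visit × 6).
- Visit: Day 28 is the first visit after Day 0 at which 10.11 has compliance computed. The result is therefore the same whether the count is cumulative or by interval. Planned dosing days are 0-27, so 28 × 6 = 168 capsules.

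The protocol states no compliance figure, so there is none to reproduce.

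**Same intake, different position of the gap**
- All doses on Days 0-13, then none. Capsules used: 14 × 6 = 84. By the formula: 84 / [(13 − 0 + 1) × 6] = 84/84 = 100%. Of planned: 84/168 = 50%.
- 84 capsules, 14-day gap in mid-interval, last dose on Day 27. By the formula: 84 / [(27 − 0 + 1) × 6] = 84/168 = 50%.

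**Varying the open gap before Day 28, every dose taken until stopping**

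| Days stopped before visit | Capsules used | Formula in 10.11 | Share of planned |
|---|---|---|---|
| 3 | 150 | 150/150 = 100% | 150/168 = 89.3% |
| 7 | 126 | 126/126 = 100% | 126/168 = 75.0% |
| 14 | 84 | 84/84 = 100% | 84/168 = 50.0% |
| 21 | 42 | 42/42 = 100% | 42/168 = 25.0% |

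In general, with an open gap of g days in an interval of L days, the formula exceeds the share of planned by the factor L/(L − g). For g = 7 this is 28/21 = 1.33, and for g = 14 it is 28/14 = 2.

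In a 14-day interval such as Days 28-42, counted by interval, stopping 7 days early gives 42/42 = 100% against 42/84 = 50%.

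**Two boundary checks**
- Earlier misses do lower the score, but it stays inflated. With 76 of 84 capsules taken and then a stop after Day 13, the formula gives 76/84 = 90.5%, against 76/168 = 45.2% of planned.
- If the patient who stopped after Day 13 takes 2 capsules on site at Day 28, and that day is used as the last-dose day, the result is (84 + 2) / [(28 − 0 + 1) × 6] = 86/174 = 49.4%. The gap is captured.

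**Day 0.** If only one 200 mg dose has been taken when compliance is computed, the formula gives 2 / (1 × 6) = 33% for a patient who has missed nothing.

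**The case against.** Several objections have force.

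*The lapse is recorded elsewhere.* The diary holds the date and time of each dose (10.1), interruption dates and durations go into the eCRF (10.5), unused drug is returned and counted (10.5, 10.7), and bottles are inspected (10.11). A site that counts 84 unused capsules at Day 28 will see what happened. This stands: the lapse is missing from the ratio, not from the data.

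*On-site dosing may close the gap.* Both stages have dosing on site at Day 28, and Stage 2 also at Days 42 and 56 (9.1.3.4 to 9.1.3.6, 10.3). If that dose is taken and counted as the last one, the figure is about right. This also stands, and it limits the defect to gaps still open at computation. The protocol does not say whether the on-site dose enters the count.

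*Ending at the last dose suits a quantity described as exposure.* That is reasonable once a patient has formally come off drug. It is not reasonable as a measure of adherence while treatment is still planned.

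A reader might infer more than the protocol supports:
- That a patient who stops on their own cannot be withdrawn for it. Section 9.3.3, item 7, is a judgement without a threshold. Item 8 separately covers interruptions of more than a week, subject to the investigator and Medical Monitor, and the 14-day example would fall under it.
- That such patients cannot be excluded from the per-protocol set. Section 14.2.1 defines that set by major protocol violations and does not mention this ratio.
- That tolerability is overstated. Safety is assessed from adverse events, laboratory results, examination, vital signs and ECG (Sections 13 and 14.2.4), not from compliance.
- That failures in unexposed patients are wrongly charged to the drug. That follows from the evaluable population, which needs one dose and a valid baseline scan (14.2.1). A different compliance denominator would not change it.

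**Conclusion.** The point holds within narrow limits. As written, Section 10.11 leaves out of the denominator any dosing gap still open when compliance is computed. A patient fully adherent until stopping scores 100% whatever the length of the gap. In the 28-day examples the true share of planned is between 89.3% (3 days) and 25.0% (21 days), and identical intake scores 100% or 50% depending only on the position of the gap.

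The conclusion rests on three assumptions: that the last dose means the last one taken, which is the natural reading of a count of days exposed; that no on-site dose at the visit is used as the last dose; and, for the exact 100%, that no earlier doses were missed.

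The effect is confined to the compliance figure and whatever is based on it. The primary endpoint, the two-stage decision rules, alpha and power do not use it. The conflict over Visit 2 is real but secondary. The correction is worth making because the formula is fixed in the protocol, gives a misleading number in the situation it should detect, and is cheap to repair.

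**What to change.** In Section 10.11, define the denominator as planned dosing days multiplied by planned capsules per day. Planned dosing days should run from the first dose, or from the previous compliance visit, to the last planned dosing day before the current visit, or to the documented discontinuation date if that is earlier. That date should be the date of the decision to discontinue; if it is set equal to the last capsule taken, the defect returns.

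The text must also say how protocol-directed holds count. Either exclude those days from planned days or report them separately. Otherwise a patient correctly on hold for the last 7 of 28 days would score 126/168 = 75%; with the hold days excluded the figure is 126/(21 × 6) = 100%. With this definition an on-site dose at the visit falls in the next interval and no longer alters the result.

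Reconcile the compliance visits in 10.11, which leaves out Visit 2, with Table 9.1 and Sections 9.1.3.2 and 9.1.3.3, which require compliance at Day 0 and Visit 2.

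The cost is short edits to 10.11 and to the schedule. Visit dates, capsule counts, interruption dates and discontinuation dates are already collected. Reported compliance will look somewhat less favourable.

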10.5 Dose Modification

The guidelines for dose modification and management of drug toxicity are as follows:

Table 10.1 Dose Modification and Management of Drug Toxicity Guidelines

Event	Grade	Management/Action
All non-hematologic and hematologic adverse events that are study drug-related	1 or 2	No change.
	3	Suspend treatment. Treatment may resume if toxicity is resolved to grade ≤ 1 or returns to baseline within 7 days. Treatment should resume at a reduced dose (100 mg t.i.d). If toxicity lasts more than 7 days, study drug will be permanently discontinued (subject to investigator and Medical Monitor agreement); if a patient experiences another grade ≥ 3 toxicity at the reduced dose, then study drug will be permanently discontinued.
	4	

Treatment may be withheld for up to 7 days due to study drug-related toxicities. Patients will be permanently discontinued from the study drug if treatment interruption is more than 7 days and the investigator and Medical Monitor consider that permanent cessation of study drug is necessary. If a patient resumes treatment before the end of a cycle, the patient will have to complete the rest of the treatment of that cycle.

When patients are suspected to experience Grade 3 or more AEs, they should contact the site as soon as possible for an appointment and bring back any unused study drug to the site. Treatment should only be withheld for nausea, vomiting, and diarrhea of Grade ≥ 3 if symptoms remain at Grade ≥ 3 despite adequate treatment. If dose modification is deemed necessary, the unused study drug will be retrieved and a new bottle with quantity of study drugs calculated based on the modified dose will be dispensed. Sufficient study drug should be dispensed for the period from the day of dose modification to the next dispensing visit.

The quantity given will be recorded in the eCRF and the drug accountability log. At the time the patient returns the unused study drug, they will be counted at the site and recorded in the eCRF. The dates and durations of any dosing interruptions will be recorded in the eCRF.

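### The compliance formula for dose-modified patients adds two ratios and leaves the exposure days ambiguous, so full adherence can score 200%, or below 100% after a protocol-directed suspension

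*Protocol*

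**What the plan says.** Protocol Section 10.11 gives two formulae. For a patient whose dose is never changed, compliance is capsules used divided by the product of exposure days and planned capsules per day. The exposure term is defined once: "The number of days patients exposed to study drug is calculated as" the day of last dose minus the day of first dose, plus 1. Nothing is subtracted for days off drug.

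For the others the section says: "Patients who undergo dose modifications will have their treatment compliance calculated by this formula". The formula is a sum of two brackets. Each has capsules used on top and the same exposure-day term below. The first denominator carries the qualifier "planned number of capsules per day for each day patient was on original dose" and the second "planned number of capsules per day for each day patient was on modified dose". There is no weighting, no averaging and no pooled denominator.

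Section 10.5 describes how a patient reaches the second formula. Drug-related Grade 3 or 4 toxicity leads to suspension, and treatment may then resume at a reduced dose. The section adds: "Treatment may be withheld for up to 7 days due to study drug-related toxicities". It also has the dates and durations of interruptions recorded in the eCRF.

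Section 9.3.3 lists as a ground for removal: "Non-compliance with study drug, protocol requirements, or study-related procedures". No numerical level of compliance is given there or in Section 10.11.

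**The concern.** A compliance measure should return 100% for a patient who takes every prescribed capsule, and should use one scale for all patients. A sum of two used-over-planned ratios does not do this unless the two denominators share a common total, and the text does not settle whether they do.

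The definition of exposure days raises a separate difficulty. It is a calendar span. Patients who reach the two-term formula have typically been through a suspension under Section 10.5. If the span covers that gap, following the protocol is scored as missing doses.

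Site staff calculate and record compliance visit by visit during the trial, so a faulty rule affects the values as they are produced. The risk runs both ways: a patient who followed instructions can look non-adherent, and a patient who missed many doses can look fully adherent.

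**Working it through.** The protocol states no compliance figure to reproduce, so the printed formula is evaluated for patients whose true adherence is known.

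**Inputs from the protocol.** The capsule is 100 mg (Section 10.6). The starting dose is 200 mg t.i.d. (Section 9.2.1), which is 6 capsules a day. The reduced dose is 100 mg t.i.d. (Section 10.5), which is 3 capsules a day. A suspension lasts up to 7 days (Section 10.5). The first treatment cycle is 84 days.

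**Assumption.** The protocol does not say how long a patient spends on each dose. Several splits are tried. Write d1 for days at the original dose, g for days suspended, d2 for days at the reduced dose, and D = d1 + g + d2.

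**Reading A, capsules and days per dose period.** With full adherence:

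6·d1/(6·d1) + 3·d2/(3·d2) = 1 + 1 = 200%, whatever d1, g and d2 are.

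For 42 days at each dose: 252/252 + 126/126 = 2.0. If half the capsules are taken: 126/252 + 63/126 = 1.0.

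**Reading B, the defined span D in both denominators.** With full adherence:

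6·d1/(6·D) + 3·d2/(3·D) = (d1 + d2)/D = (D − g)/D.

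- No suspension, 42 + 42 days: 252/504 + 126/252 = 0.5 + 0.5 = 100%.
- 35 days, 7 suspended, 42 days: 210/504 + 126/252 = 77/84 = 91.7%.
- 14 days, 7 suspended, 7 days: 84/168 + 21/84 = 21/28 = 75.0%.

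**Pooled ratio.** Total capsules used divided by (6·d1 + 3·d2), with suspended days contributing zero.

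| d1 / g / d2 (days) | True adherence | Reading A | Reading B | Pooled |
|---|---|---|---|---|
| 42 / 0 / 42 | 100% | 200% | 100% | 100% |
| 35 / 7 / 42 | 100% | 200% | 91.7% | 100% |
| 14 / 7 / 63 | 100% | 200% | 91.7% | 100% |
| 14 / 7 / 7 | 100% | 200% | 75.0% | 100% |
| 10 / 7 / 11 | 100% | 200% | 75.0% | 100% |
| 35 / 7 / 42 | 80% | 160% | 73.3% | 80% |
| 42 / 0 / 42 | 50% | 100% | 50% | 50% |

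**Single-ratio formula.** For a patient who stays on 6 capsules a day and has g days off drug between first and last dose, the value is 6·(D − g)/(6·D) = (D − g)/D. This is the same shortfall as under Reading B.

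**The case against.** The best defence is that 200% is not the only reading. Section 10.11 defines exposure days once and uses the same term in both brackets. The trailing qualifiers can be taken to say only which capsule count applies. Read that way, an uninterrupted patient scores 100%. This stands as far as it goes: the text is ambiguous, and 200% is one outcome of it. It does not rescue the formula, because a patient normally arrives at the reduced dose through a suspension, and Reading B then falls short of 100%.

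A reader might infer that the two faults apply together: a doubled score, with suspension days counted as missed on either reading. The documents do not support that. Under Reading A each period runs from its own first dose to its own last, so the gap falls in neither denominator. The faults combine only if the gap is assigned to the original-dose period. The result for the suspended splits tried is then about 159% to 183% (for example 210/252 + 126/126 = 183.3%), not 200%.

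A reader might also quote 7/14 = 50% for a suspension between the Day 28 and Day 42 visits. That needs Reading B, exposure days restarted at each visit, and doses on both sides of the gap within those 14 days. Section 10.11 does not say that the count restarts. Counted from first dose, the Day 42 value would be 35/42 = 83%.

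A third inference is that the formula pushes patients into failure on the primary endpoint. No cut-off links the value to removal. Interruptions longer than a week have their own rule, which needs the judgement of the investigator and Medical Monitor (Sections 9.3.3 and 10.5). Section 14.2.2.1 does not use compliance, and no analysis population in Section 14.2.1 names it.

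The reach is narrow as well. In the 13-patient Phase 1 study (Section 7.4) there were no Grade 4 events, and the Grade 3 events were judged unrelated to drug.

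Finally, how to treat suspended days is a derivation convention that an analysis plan could settle. That is true of the reported summaries. But the protocol itself fixes the formula and has site staff record the result, so an analysis plan alone would not correct the values produced at sites.

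**Conclusion.** The point holds as a minor error in a stated rule. The formula for dose-modified patients is ambiguous, and on either of the two readings above it returns a wrong value for a fully adherent patient who is suspended for 7 days and resumes at the reduced dose. The value is 200% with per-period capsules and days. With the defined span in both terms it is about 92% over 84 days or 75% over a 28-day window. On the per-period reading, a patient who took half the capsules scores 100%, so real non-adherence is hidden.

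The 200% does not depend on the assumed period lengths. The 92% and 75% depend on the length of the window and on a full 7-day suspension lying between first and last dose.

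The effect is on recorded and reported compliance. Any effect on withdrawal under item 7 of Section 9.3.3 is indirect, and nothing in the documents ties the formula to the primary endpoint.

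**What to change.** Replace both formulae in Section 10.11 with one that applies to every patient: total capsules used in the interval divided by total capsules prescribed in it. Prescribed capsules are the sum, over the days of the interval, of the capsules per day in force, with zero for days suspended on protocol instruction. State whether the interval runs from first dose or from the preceding visit.

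The pooled ratio gave 100% for full adherence in every split tried, and returned 50% and 80% for patients who took those shares. It puts modified and unmodified patients on one scale and changes no dose or stopping rule.

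The cost is one formula. Section 10.5 already has the quantities dispensed, the capsules returned, and the dates and durations of interruptions recorded in the eCRF, so no new data are needed and values already recorded can be recalculated.
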